#### 1 PROTOCOL SYNOPSIS

**Population:** Healthy adult males and females

**Total number of participants:** 75 enrolled participants (25 per group)

#### 1.1 Inclusion Criteria

- 1. Males and females between 40 and 80 years of age, inclusive
- 2. Female participant is not of child-bearing potential, defined as females who have undergone a sterilization procedure (e.g. hysterectomy, bilateral oophorectomy, bilateral tubal ligation, complete endometrial ablation) or have been post-menopausal for at least 1 year prior to screening

Or,

Females of child-bearing potential must have a negative baseline urine pregnancy test and agree to use a medically approved method of birth control for the duration of the study. All hormonal birth control must have been in use for a minimum of three months. Acceptable methods of birth control include:

- Hormonal contraceptives including oral contraceptives, hormone birth control patch (Ortho Evra), vaginal contraceptive ring (NuvaRing), injectable contraceptives (Depo-Provera, Lunelle), or hormone implant (Norplant System)
- Double-barrier method
- Intrauterine devices
- Non-heterosexual lifestyle or agrees to use contraception if planning on changing to heterosexual partner(s)
- Vasectomy of partner at least 6 months prior to screening
- 3. Participants who have not yet but are willing to receive the influenza vaccine
- 4. Agrees to provide a verbal history of flu vaccination
- 5. Agrees to maintain current lifestyle habits as much as possible throughout the study depending on your ability to maintain the following: diet, medications, supplements, exercise, and sleep and avoid taking new supplements
- 6. Healthy as determined by medical history and laboratory results as assessed by Qualified Investigator (OI)
- 7. Willingness to complete questionnaires and diaries associated with the study and to complete all clinic visits
- 8. Provided voluntary, written, informed consent to participate in the study

#### 1.2 Exclusion Criteria

- 1. Women who are pregnant, breast feeding, or planning to become pregnant during the study
- 2. Participant has a known allergy to the active or inactive ingredients in UP360, UP446, placebo, or QIV
- 3. Unvaccinated participants with flu prior to baseline from September 2020 or prior to Day 28 vaccination
- 4. Participants self-reporting a diagnosis of COVID-19 prior to baseline or prior to Day 28 vaccination
- 5. Participants who have received the COVID-19 vaccine
- 6. Current use of prescribed immunomodulators (including corticosteroids) such as immunosuppressants or immunostimulants within 4 weeks of baseline (see Section 7.3)
- 7. Current use of dietary supplement or herbal medicines associated with boosting or modulating the immune system unless willing to washout (see Section 7.3.2)

Protocol 21UIHU A randomized, triple-blind, placebo-controlled, parallel clinical trial to investigate two products on supporting immune function in healthy adults

- 8. Participation in other clinical research studies 30 days prior to enrollment will be assessed on a case-by-case basis by the QI
- 9. Individuals who are unable to give informed consent
- 10. Any other condition, chronic disease, or lifestyle factor, that, in the opinion of the QI, may adversely affect the participant's ability to complete the study or its measures or pose significant risk to the participant

# 1.3 Schedule of Assessments

Procedures/Assessments	Screening	Baseline Day 0	Day 28 ± 2 days	Day 56 ± 2 days
Informed consent	X			
Review inclusion/exclusion criteria	X	X		
Review medical history	X			
Urine pregnancy test		X		X
Review concomitant therapies	X	X	X	X
Heart rate and blood pressure		X	X	X
Height* and weight *only analyzed at baseline		X		X
Randomization		X		
Blood collection for analysis of CBC, electrolytes (Na, K, Cl), HbA1c*, glucose, eGFR, creatinine, AST, ALT, ALP, and bilirubin *only analyzed at screening	X	X	X	X
Blood collection for analysis of ESR, CRP, complement C3, complement C4, IgA, IgG, IgM, immune cell phenotypes (CD3+, CD8+, CD4+, CD45+, TCRγδ, CD3-CD16+CD56+)		X	X	X
Blood collection for future analysis of cytokines, HMGB1, NF-κB, Nrf-2, 8-iso-prostaglandin F2α, CAT, GSH-Px, SOD, MDA, AGEs, HI titers for specific strains of virus		X	X	X
Modified WURSS-24 Questionnaire dispensed	X	X	X	
Modified WURSS-24 Questionnaire returned		X	X	X
Vitality Questionnaire completed		X	X	X
COVID-19 Impact on QoL Questionnaire completed		X	X	X
Flu vaccine administered			X	
IP dispensed		X	X	
IP returned			X	X
Study Diary dispensed	X	X	X	
Study Diary returned		X	X	X
Compliance calculated			X	X
Adverse Events	X	X	X	X

#### 2 LIST OF ABBREVIATIONS

Degrees

ΑE Adverse Event

advanced glycation end-products **AGEs** 

ALT Alanine Aminotransferase **ALP** Alkaline Aminotransferase **AST** Aspartate Aminotransferase Area Under the Curve AUC

BP **Blood Pressure** 

C Celsius Ca Calcium catalase (CAT CAT

CBC Complete Blood Count Cluster of Differentiation CD

Cl Chloride

COVID-19 Coronavirus Disease 2019

**CRF** Case Report Form

Contract Research Organization CRO

CRP C-reactive Protein

DIN **Drug Identification Number** 

Date of Birth DOB

**EDTA** Ethylenediaminetetraacetic Acid Electronic Case Report Form **eCRF** Glomerular Filtration Rate eGFR Erythrocyte Sedimentation Rate **ESR** 

"and so forth" etc. "for example" e.g. "and others" et al Gram

g

**GCP** Good Clinical Practice GSH-Px glutathione peroxidase HI Hemagglutinin inhibition

Human Immunodeficiency Virus HIV HMGB1 High Mobility Group Box 1

Heart Rate HR Pounds lbs.

Informed Consent Form **ICF** 

International Conference of Harmonization **ICH** 

"in other words" i.e.

**Independent Ethics Committee** IEC

Immunoglobulin A **IgA** IgG Immunoglobulin G Immunoglobulin M **IgM** IΡ **Investigational Product** Institutional Review Board IRB

ITT Intent to Treat K Potassium Kilogram kg

MCC Microcrystalline cellulose Protocol 21UIHU A randomized, triple-blind, placebo-controlled, parallel clinical trial to investigate two products on supporting immune function in healthy adults

MCH Mean Corpuscular Hemoglobin

MCHC Mean Corpuscular Hemoglobin Concentration

MCV Mean Corpuscular Volume

MDA malondialdehyde

mg milligram

mmHg Millimeter of Mercury

mL Milliliter MS Microsoft Na Sodium

NF-κB Nuclear Factor Kappa B

Nrf-2 Nuclear Factor Erythroid 2-Related Factor 2

OTC Over the Counter PCP Primary Care Physician

PP Per Protocol

QI Qualified Investigator

QIV Quadrivalent Influenza Vaccine

QoL Quality of Life RBC Red Blood Cells

RDW Red Blood Cell Distribution Width

SAE Serious Adverse Event SOD superoxide dismutase

SOPStandard Operating ProcedureTCRγδ+T-Cell Receptor Gamma DeltaTPDTherapeutics Products Directorate

UAT User Acceptance Testing ULN Upper Limit of Normal

URTI Upper Respiratory Tract Infection

WBC White Blood Cell

WHO World Health Organization

WURSS Wisconsin Upper Respiratory Symptom Survey

#### 4 INTRODUCTION

Acute respiratory tract infections are a leading cause of morbidity and mortality globally, illustrated by seasonal flu epidemics and most recently COVID-19, caused by the SARS-CoV2 infection. Every year influenza causes an estimated one billion infections leading to three to five million severe cases, and 290,000 to 650,000 deaths worldwide (1). In Canada, it is the leading cause of death due to a vaccine-preventable disease (2) with 3,500 mortalities per year (3). In the United States and Canada, the flu season occurs in the fall and winter, peaking anywhere from late November through March (2). During these months, influenza increases the demand on the healthcare system with 12,000 hospitalizations occurring annually (4). The prevalence of the flu during this period also translates into billions of dollars in lost revenue and worker productivity annually with over 45 million days of work lost annually due to the common cold, translating into an estimated \$40 billion USD lost to both direct and indirect costs (5).

To combat this, vaccination against the flu has been adopted by many countries as the gold standard for prevention. In Canada, the national influenza vaccination coverage goal is 80% of those at risk of influenza-related complications or hospitalization are vaccinated. However, in the previous three years, only approximately 40% of Canadian adults received the flu vaccine, with the rate of vaccination amongst healthy adults between 18-64 years of age even lower at 27-31% (6).

This year, there is far greater strain on the health care system due to the COVID-19 pandemic as co-infection with COVID-19 and influenza or other respiratory pathogens is a significant risk factor for prolonged hospitalization (7, 8). Amid this public health crisis, it is critical to minimize the burden of influenza on the Canadian healthcare system so resources can be allocated appropriately. Further, a recent study has suggested that influenza vaccination in an older population over the age of 65 is negatively associated with COVID-19 mortality (9), supporting the importance of vaccination during this time. These significant public health implications point to the urgent need to increase vaccine adoption. In addition to low adoption rates, the Centers for Disease Control and Prevention estimated the current vaccine to be approximately 45% effective in preventing the influenza (10). This is consistent with previous years, with efficacy between 19-54% (11). This suggests that these is great need to find therapies that may increase the efficacy of the flu vaccine and reduce the severity and duration of upper respiratory tract infections (URTIs) including the flu and common cold.

The immune system is comprised of two arms which differ in their response: innate which is fast acting and non-antigen specific, and adaptive, or acquired, which is slower to respond but antigen-specific. The innate immune system involves physical barriers such as skin, the complement system and immune cells with phagocytic capacity (neutrophils, macrophages, Natural Killer cells). These innate immune cells are able to quickly respond and destroy foreign pathogens generally through inflammatory process, however they lack the ability to increase efficacy or speed of response to a reoccurring pathogen (12). After the innate immune response, the adaptive immune system is engaged and able to develop immunological "memory" to repeated exposure. The cells of the adaptive immune system include T cells, or lymphocytes, which are responsible for initiating the adaptive response and killing virally-infected cells, and B lymphocytes which produce immunoglobulins (Ig) to target specific pathogens (12). Vaccines provide protection against repeated pathogen exposure through development of immunological memory (13).

It is well established that various nutrients including vitamin A, B12, folate, selenium, iron, copper and omeg-3 fatty acids play an important role in supporting the immune system and optimal nutritional status is key in protection against viral infections (14). Further, the addition of adjuvant supplements or nutritional

A randomized, triple-blind, placebo-controlled, parallel clinical trial to investigate two products on supporting immune function in healthy adults

interventions have been investigated to improve the immune response to influenza and efficacy of the influenza vaccine (15-18). A vaccine model is used to examine if prophylactic supplementation modulates the immune response that is induced by the immunological challenge of administering the vaccine (17, 19).

To examine the role of dietary supplements in supporting immune function in response to influenza vaccination using this vaccine model, there are two investigational products (IPs) being used in the current study. One product, UP360, includes ingredients *aloe vera* gel powder, rosemary and *Poria cocos* extracts and the other, UP446, contains *Acacia catechu* (*Senegalia catechu*) and *Scutellaria baicalensis*. Through distinct mechanisms of action, these ingredients have been shown to activate the immune system, reduce inflammation and oxidative stress and protect against lung damage.

Aloe vera contains a variety of bioactive ingredients including vitamins, minerals, anthraquinones and polysaccharides that have antioxidant, anti-inflammatory and anti-bacterial effects (20-23). Studies in vitro have shown that aloe polysaccharide inhibits the replication of the H1N1 influenza virus (20) and animal models have demonstrated reduction in viral load and clinical symptoms of influenza infection (20) and increased survival and Ig production following influenza immunization (24). Several components of rosemary have been shown to have immunomodulatory effects in vitro and in animal models (25), primarily through increasing the IgM and IgG response following immune challenges (26). Portia cocos is a medicinal mushroom also known as fuling, matsuhodo, poria or China root. The major bioactive is the polysaccharide β-glucan that has been shown to have anti-inflammatory and immunomodulatory effects (27), with activation of T cells a potential mechanism of action. The adjuvant activity of *Portia cocos* has been examined in a variety of animal models with rabies, H1N1 influenza and hepatitis B vaccines (28, 29). The flavonoid extracts of Senegalia catechu and Scutellaria baicalensis has been demonstrated to reduce pro-inflammatory gene expression in vitro (30) and in rodent models Senegalia catechu has been shown to have anti-inflammatory activity and increase antibody titre after immunization (31). While these in vitro and in vivo studies suggest these ingredients have effects on immune function, there is a dearth of evidence on the immunomodulatory effects with human vaccine models in randomized, double-blind, placebocontrolled clinical trials.

The objective of this randomized, triple-blind, placebo-controlled, parallel study is to investigate two products, UP360 and UP446, compared to a placebo on supporting immune function in a healthy adult population. The increase in lymphocyte populations and Ig production with supplementation of the IPs compared to placebo will be compared in the 28-day pre- and post-vaccination periods to examine the immune boosting effects of the products. Other quantitative markers of immune function will be measured including erythrocyte sedimentation rate (ESR), C-reactive protein (CRP) and complement C3 and C4 proteins. To support the alterations in immunity, the Wisconsin Upper Respiratory Symptom Survey (WURSS)-24 will be used as a subjective measure of signs and symptoms of URTI, inclusive of cold, flu and COVID-19. The impact of COVID-19 on wellbeing and quality of life will also be assessed to examine the potential confounder of the pandemic on immune function. The findings of this study will provide evidence for UP360 and UP446 to support immune function with flu vaccination, understand external factors that influence immunity during the cold and flu season and COVID-19 pandemic and potentially inform public health policy regarding community spread influenza and COVID-19.

Participants will be healthy men and women who have not been vaccinated with the quadrivalent influenza vaccine (QIV) but are willing to receive it during this study. Participants will be between the ages of 40 to 80 years old to include older adults that are the target of national vaccination programmes and those potentially most likely to have reductions in COVID-19 mortality with influenza vaccination. Participants'

Protocol 21UIHU A randomized, triple-blind, placebo-controlled, parallel clinical trial to investigate two products on supporting immune function in healthy adults

medical history, lifestyle factors and laboratory results will be reviewed to assess eligibility and may be excluded if there is any condition or lifestyle factor that the QI determines may affect study measures or safety of the participant. To avoid interactions with the active ingredients in the IPs, participants on medications will be assessed on a case-by-case basis to ensure their eligibility and safety with special reference to the medications listed in the Investigational Brochure. All participants will be asked to maintain their current diet, medication, supplements, exercise and sleep while avoiding taking any new supplements during the study to avoid confounders. Information regarding occupation, social interactions, history of flu vaccination, URTIs, allergies, and lifestyle factors will be collected to account for inter-individual variability on study outcomes. The inclusions and exclusions in this study will ensure only participants who are healthy, stable, and have no comorbidities are enrolled.

#### 5 STUDY OBJECTIVES

The objective of this study is to investigate the efficacy of two investigational products (IPs), UP360 and UP446, on supporting immune function in healthy adults.

#### **Primary outcome:**

The difference between UP360, UP446 and placebo in the increase in immune parameters as assessed by lymphocyte populations (CD3+, CD4+, CD8+, CD45+, TCRγδ+, CD3-CD16+56+) and immunoglobulins (IgG, IgM, and IgA) in blood from baseline at Day 28 and 56

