#### 11 STATISTICAL EVALUTION

#### 11.1 Determination of Sample Size

The planned total sample size will be 75 with 25 participants randomized to each study group. This sample size will enable detection of a difference in CD3+ of 10.8%, difference in CD4+ of 6.5%, difference in CD8+ of 4.9%, difference in CD45+ of 16.7% and difference in NK cells (CD56+) of 4.4% for lymphocytes; difference in IgA of 67 mg/dL (0.67 g/L), difference in IgG of 440 mg/dL (4.4 g/L), and difference in IgM of 133 mg/dL (1.33 g/L) for and immunoglobulins among the three arms at an overall 5% significance level and 80% power. This sample size takes into account a loss to follow up rate of 20%. The calculation is based on the studies by Olivares et al (19, 36, 37).

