# 11.3 Statistical Analysis Plan

All the primary and secondary endpoints will be analyzed as continuous variables.

For each primary and secondary endpoint, descriptive statistics including number of subjects, arithmetic mean, standard deviation, median, minimum and maximum values will be presented for each study day and for the changes from baseline (Day 0) to each subsequent study day.

Changes in continuous endpoints from baseline will be calculated as:

Change to 
$$V_i = Value$$
 at  $V_i - Value$  at  $V_{baseline}$ 

Differences in changes between groups will be assessed by repeated measures mixed model ANOVA, with study group and visit as the fixed effects. Each model will include the baseline value as a covariate. Within group changes will be assessed by the paired t-test or Wilcoxon Sign Rank test, depending on the distribution of the data. All tests of significance for primary outcomes will be performed at one-sided, and for secondary outcomes will be performed at two-sided, alpha level = 0.05 unless otherwise specified.

The co-primary outcomes will be interpreted individually and together as a real-life global assessment of immune function. As such, there will be no adjustment for multiple outcomes (38-42). This is in accordance with the following principles of the American Statistical Association's statement on statistical significance

and p-values: #3 – "scientific conclusions and business or policy decisions should not be based only on whether a p-value passes a specific threshold;" #4 – "proper inference requires full reporting and transparency;" and #6 – "by itself, a p-value does not provide a good measure of evidence regarding a model or hypothesis" (43).

Missing data for the primary and secondary endpoints will be imputed with last-observation-carried-forward (LOCF) method or multiple imputation as a sensitivity analysis for ITT Population. No imputation will be performed for PP and Safety Population.

Probabilities  $\leq 0.05$  will be considered statistically significant. All statistical analysis will be completed using the R Statistical Software Package Version 3.6.3 or newer for Microsoft Windows (44).

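### The protocol asks whether each product beats placebo, but its primary outcome, sample-size basis and analysis never fix the two product-versus-placebo contrasts as primary

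*Protocol*

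**What the plan says.** The Introduction (Section 4) gives the purpose as "to investigate two products, UP360 and UP446, compared to a placebo on supporting immune function in a healthy adult population". It adds that increases in lymphocytes and immunoglobulins on the products will be set against placebo. Section 5 states the objective as the efficacy of the two products.

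Three operative statements are worded differently:

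- **Section 5, primary outcome:** "The difference between UP360, UP446 and placebo in the increase in immune parameters as assessed by lymphocyte populations", together with "immunoglobulins (IgG, IgM, and IgA) in blood from baseline at Day 28 and 56". No pair of arms is named.
- **Section 11.1:** the listed differences are detectable "among the three arms at an overall 5% significance level and 80% power".
- **Section 11.3:** "Differences in changes between groups will be assessed by repeated measures mixed model ANOVA, with study group and visit as the fixed effects". No contrast, order of testing or success rule follows.

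Section 11.3 also says "All tests of significance for primary outcomes will be performed at one-sided", at alpha 0.05. It waives adjustment for multiple outcomes and does not mention multiple arm comparisons.

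**The concern.** The question has two parts: does UP360 beat placebo, and does UP446 beat placebo? A three-level group factor carries two degrees of freedom. Its test responds to any separation among the arms, including UP360 versus UP446 and a product falling below placebo. Neither of those shows efficacy.

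A one-sided rule needs a signed contrast. A test on two degrees of freedom has no sign, so the stated model term and the stated sidedness cannot both describe the primary test. If the rule is taken to mean pairwise contrasts, the protocol still does not say which pairs count. UP360 versus UP446 is not excluded, and no direction is given for it.

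At stake is what a positive primary result would mean. Under the present wording it need not show that either product is better than placebo.

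**Working it through.** **Inputs from the protocol (Section 11.1).** 25 randomised per arm, 20% loss to follow-up, overall 5% level, 80% power. Evaluable per arm: 25 × (1 − 0.20) = 20, which is consistent with the total of 75.

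**Can the stated differences show which comparison was powered?** Section 11.1 says "This sample size will enable detection of a difference in CD3+ of 10.8%, difference in CD4+ of 6.5%, difference in CD8+ of 4.9"% and gives further values, but no SDs. With 20 per arm and 80% power, the detectable difference in SD units, and the CD3+ SD that would match the stated 10.8 points, are:

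| Basis | Detectable difference | Implied CD3+ SD (10.8 ÷ difference) |
|---|---|---|
| Group F test, 0.05, means 0, d/2, d | 1.01 SD | 10.7 |
| Group F test, 0.05, means 0, 0, d | 0.87 SD | 12.4 |
| One product vs placebo, one-sided 0.05 | 0.80 SD | 13.5 |
| One product vs placebo, one-sided 0.025 | 0.91 SD | 11.9 |

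Every basis fits for some SD, so the sample size does not settle the matter.

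**What the group test would show if it were the primary result.** Assumptions: one marker, one visit, normal data, unit SD, no baseline covariate, 20 per arm. True means are placebo 0, one product 0, the other −0.8 SD.

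- The mean of the three arms is −0.267. The sum of squared deviations is 0.8² × 2/3 = 0.427. Noncentrality = 20 × 0.427 = 8.53.
- The critical F on 2 and 57 degrees of freedom at 0.05 is 3.16. Power = 72%, and simulation agrees.
- Here 'above placebo' means a pooled-SD contrast significant at one-sided 0.05. In simulation the group test is significant with neither product above placebo in about 67.5% of all trials: 67.5 ÷ 72 = 94% of the significant ones.
- With a shortfall of 0.5 SD, the group test is significant in 34% of trials, and in 30% of all trials it is significant with neither product above placebo.
- If success required a directional contrast against placebo, the success rate in either case would be about 5% at one-sided 0.05 and about 2.5% at one-sided 0.025.

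**Error rate of two contrasts.** The two contrasts share the placebo arm. With no true effect, two unadjusted one-sided 0.05 tests give at least one false positive in about 8.6 to 8.8% of trials (if they were independent, 1 − 0.95² = 9.75%). At one-sided 0.025 each, the figure is about 4.6%.

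**The case against.** The strongest reply is that Section 11.3 names a model, not a decision rule. Placebo contrasts come from the same fit. The one-sided rule makes sense only for directional contrasts, and both the Introduction and the primary outcome speak of an increase. This stands: the protocol does not state that the group F test decides the primary outcome, and a reader who infers that goes beyond the text. What the reply does not supply is the list of pairs, or any exclusion of UP360 versus UP446.

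A reader might also infer that the products are likely to move these markers in opposite directions. The Introduction does not support that. It says of both products' ingredients that "Through distinct mechanisms of action, these ingredients have been shown to activate the immune system, reduce inflammation and oxidative stress", and for UP446 it cites raised antibody titre after immunisation in rodents alongside reduced pro-inflammatory gene expression. Nothing in it points to lower lymphocytes or immunoglobulins on UP446.

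Nor should a scenario with one product at +0.4 SD and the other at −0.4 SD be read as false efficacy. There the group test is significant in 59% of trials, and in about half of those neither contrast with placebo is significant. But one product truly exceeds placebo, so this largely reflects low pairwise power.

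Last, a statistical analysis plan could name the contrasts. It could not do so without narrowing a primary outcome and sample-size basis that the protocol already fixes.

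**Conclusion.** The point holds as a badly fixed primary comparison, not as a wrong objective or an established omnibus primary test. The intended comparison can be recovered from the Introduction, but Sections 5, 11.1 and 11.3 do not carry it through, and the one-sided rule conflicts with the only group term described.

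The 72% and 94% are conditional on reading the group test as the primary result and on an assumed 0.8 SD shortfall, in a simplified single-visit model. They show how far a significant group test can be from evidence of efficacy. They do not predict this trial. The logical point, that a group effect on two degrees of freedom does not imply superiority of either product to placebo, needs none of those assumptions. The change is worth making before analysis.

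**What to change.** - **Sections 5 and 11.3:** name UP360 minus placebo and UP446 minus placebo, estimated from the planned mixed model, as the primary comparisons. State the direction. State error control across the two that is consistent with the overall 5% in Section 11.1, for example one-sided 0.025 each or Dunnett's method.
- **Section 11.3:** declare the three-level group test and UP360 versus UP446 exploratory, with no efficacy conclusion.
- **Section 11.1:** state that the detectable differences refer to each product versus placebo at that alpha, and restate them if they were computed on another basis.

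This settles only which arms are compared. It does not address the nine primary variables at two visits.

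**Cost.** Wording in three sections, with the same model and no new data. Product-versus-product results become exploratory. The detectable differences may become slightly less favourable: at one-sided 0.025 each, 0.91 SD against 0.80 SD for an unadjusted one-sided 0.05 contrast, or against 0.87 to 1.01 SD if a group test was the basis.
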